5.2 Exclusion Criteria

Participants are excluded from the study if any of the following criteria apply:

Medical Conditions

- 1 Cohort 1: Significant infection or other acute illness, including fever > 100 °F (> 37.8 °C) on the day prior to or day of receiving AZD7442.
- 2 History of infection with SARS-CoV-1 or MERS-CoV.
- 3 Cohorts 1 and 2: Current need for immediate medical attention in an emergency room service in the clinical opinion of the site Investigator or current need for hospitalization ([Appendix E](#)) in the following circumstances:
 - (a) Due to progressive COVID-19 as this implies severe disease (an exception is participants hospitalized with mild-moderate COVID-19 as a precautionary measure for isolation/infection prevention or for the purpose of conducting study procedures).
 - (b) For any underlying medical condition that requires hospitalization (suggestive of an unstable medical condition) with the following exceptions:
 - Neonates aged \geq 29 weeks GA to < 1 month in their birth hospitalization when discharge is expected within 7 days after receiving AZD7442.

- Children hospitalized for maintenance chemotherapy administration (induction, reinduction, relapse chemotherapy excluded). AZD7442 administration is to occur a minimum of 2 hours post chemotherapy administration (including any hydration or blood products) or post the institutional standards for observation after chemotherapy administration, whichever is longer. Only children who, in the opinion of the investigator, are at low risk for a hypersensitivity reaction to administration of chemotherapy or blood products should be considered for same day administration of AZD7442 during hospitalization for maintenance chemotherapy.

- 4 Requirement for mechanical ventilation or extracorporeal membrane oxygenation or anticipated impending need for mechanical ventilation at baseline for treatment of COVID-19 (CPAP and high flow O₂ is permitted).
- 5 Known history of allergy or reaction to any component of the study drug formulation.
- 6 Previous hypersensitivity, injection/infusion-related reaction, or severe adverse reaction following administration of a mAb for any indication.
- 7 Any co-morbidity requiring surgery within 7 days prior to study entry, or that is considered life-threatening in the opinion of the site Investigator within 30 days prior to study entry.
- 8 Any other significant disease, disorder, or finding that, in the judgment of the Investigator, may significantly increase the risk to the participant because of participation in the study, affect the ability of the participant to participate in the study, or impair interpretation of the study data.

Prior Therapy (Before Enrollment)

- 9 Prior receipt of convalescent COVID-19 plasma/sera or hyperimmune globulin therapy.
- 10 Prior receipt of mAb/biologic indicated for the prevention or of SARS-CoV-2 or treatment of COVID-19 or expected receipt during the period of study follow-up.
- 11 Prior receipt of a COVID-19 vaccine ≤ 14 days before screening or plan to receive a COVID-19 vaccination ≤ 14 days after IMP administration at study Visit 1 (see Section 6.5.1). Receipt of a COVID-19 vaccine > 14 days before screening is allowed.

Other Exclusions

- 12 Employees of the Sponsor involved in the planning, execution, supervising, or reviewing the AZD7442 program, clinical study site staff, or any other individuals involved with the conduct of the study, or immediate family members of such individuals.
- 13 Judgment by the Investigator that the participant should not participate in the study if the participant is unlikely to comply with study procedures, restrictions, and requirements.

- 14 History of alcohol or drug abuse within the past 2 years that, according to the Investigator, might affect assessments of safety or ability of participant to comply with all study requirements.
- 15 Investigational Drugs or Devices: Treatment with investigational drug or device in another clinical trial within the last 30 days or 5 half-lives of the drug (whichever is longer) prior to screening. Note: Participation in observational studies (ie, studies that do not require medication, blood draws, or an additional intervention) is not exclusionary. Interventional trials which do not include investigational drugs (only include approved therapies), or investigational treatment regimens may be considered if the blood draw requirements and study interventions are minimal and not deemed by the Investigator to interfere with completion of the planned study sampling and follow-up.
- 16 Vulnerable persons (eg, ward of the state, kept in detention).

5.3 Lifestyle Considerations

- Restrictions related to concomitant medications and drugs of abuse and alcohol are described in Section 6.5.

5.4 Screen Failures

Screen failures are defined as participants who consent to participate in the clinical study but are not subsequently enrolled in the study. A minimal set of screen failure information is required to ensure transparent reporting of screen failure participants to meet the Consolidated Standards of Reporting Trials (CONSORT) publishing requirements and to respond to queries from regulatory authorities. Minimal information includes demography, screen failure details, eligibility criteria, and any SAE.

Individuals who do not meet the criteria for participation in this study (screen failure) may be rescreened if the eligibility criterion that resulted in screen failure has changed in a manner that meets eligibility.

Only a single rescreening is allowed in the study. Rescreened participants should be assigned the same participant number as for the initial screening. Individuals who are rescreened do not need to reconsent for the study.

6 STUDY INTERVENTION

Study intervention is defined as any investigational intervention(s), marketed product(s) or placebo intended to be administered to or medical device(s) utilized by a study participant according to the study protocol.

6.1 Study Interventions Administered

6.1.1 Investigational Product

All eligible participants will receive a single dose of AZD7442 on Day 1, either IM (AZD8895 followed by AZD1061 administered separately) or a single IV infusion (AZD8895 and AZD1061 co-administered), and participants will be monitored for 365 days after IMP administration (Table 7). Dose levels will be stratified by body weight range categories. Age-appropriate quantities of all excipients are used within the AZD7442 formulation. All excipients are of pharmaceutical grade and are not considered to pose any safety issues for children at the anticipated exposure levels.

Table 7 Investigational Product: AZD7442

Intervention name	AZD7442 (AZD8895 + AZD1061) (AstraZeneca)
Type	Biologic
Dose formulation	AZD7442 is comprised of 2 drug products supplied as separate vials of AZD8895 and AZD1061. Each vial contains a solution of 100 mg/mL active ingredient (AZD8895 or AZD1061), 20 mM histidine/histidine-HCl, 240 mM sucrose, 0.04% (w/v) PS80, pH 6.0. The label claim volume for each vial is 1.5 mL and each vial contains 150 mg (nominal) of active ingredient.
Unit dose strength(s)	100 mg/mL of AZD8895 in a single vial 100 mg/mL of AZD1061 in a single vial
Dosage level(s)	The dose levels are stratified by body weight range categories as shown in Table 6 (prophylaxis of COVID-19/treatment of mild to moderate COVID-19: 60 to 600 mg IM or 50 to 440 mg IV; treatment of severe COVID-19: 60 to 600 mg IV).
Route of administration	IM (AZD8895 followed by AZD1061) or a single IV infusion (AZD8895 and AZD1061 concurrently)
Use	Experimental
Sourcing	AstraZeneca
Packaging and labeling	AZD7442 will be provided in glass vials. Each glass vial will be labeled as required per country requirement.

COVID-19, coronavirus 2019; IM, intramuscular; IV, intravenous, w/v, weight per volume.

Details of the batch numbers will be included in the Trial Master File, and the final CSR. Labels will be prepared in accordance with GMP and local regulatory guidelines. The labels will fulfill GMP Annex 13 requirements for labeling.

6.2 Preparation/Handling/Storage/Accountability

- 1 Only participants enrolled in the study may receive study intervention and only authorized site staff may supply or administer study intervention. All study intervention must be stored in a secure, environmentally controlled, and monitored (manual or automated) area in accordance with the labeled storage conditions with access limited to the Investigator and authorized site staff.
- 2 The Investigator, institution, or the head of the medical institution (where applicable) is responsible for study intervention accountability, reconciliation, and record maintenance (ie, receipt, reconciliation, and final disposition records).

6.2.1 Storage and Handling Procedures

AZD7442 vials (AZD8895 and AZD1061) are stored at 2 °C to 8 °C (36 °F to 46 °F) and must not be frozen. The Investigator, or an approved representative (eg, pharmacist), will ensure that all study intervention is stored in a secured area, in refrigerated temperatures (2 °C to 8 °C; 36 °F to 46 °F) and in accordance with applicable regulatory requirements. A temperature log will be used to record the temperature of the storage area. Temperature excursions outside the permissible range listed in the clinical supply packaging are to be reported to the monitor upon detection. A calibrated temperature monitoring device will be used to record the temperature conditions in the drug storage facility. Storage conditions stated in the IB may be superseded by the label storage.

AZD7442 must be kept in original packaging until time of preparation to prevent prolonged light exposure.

AZD7442 is comprised of 2 drug products supplied as separate vials of AZD8895 and AZD1061. The product is a clear to slightly opalescent, colorless to slightly yellow solution.

Each vial selected for dose preparation should be inspected. If there are any defects noted with the IMP (ie, it is visually different to the description provided above), the Investigator and site monitor should be notified immediately.

The dose of AZD7442 (AZD8895 and AZD1061) for administration must be prepared by the Investigator's or site's designated IMP manager using aseptic technique. Total time from needle puncture of the vial to the start of administration must not exceed:

- 24 hours at 2 °C to 8 °C (36 °F to 46 °F)
- 4 hours at room temperature.

If the final product is stored at both refrigerated and ambient temperatures, the total time must not exceed 24 hours, otherwise a new dose must be prepared from new vials. AZD7442

(AZD8895 and AZD1061) does not contain preservatives; any unused portion of the vial must be discarded immediately after use.

No incompatibilities between AZD7442 (AZD8895 and AZD1061) and the following component materials of construction have been observed:

- IV bags made of polyvinylchloride (PVC) or polyolefin (PO)
- Polypropylene (PP) syringes
- Filters made of polyethersulfone (PES)

AstraZeneca will be permitted upon request to audit the supplies, storage, dispensing procedures and records.

6.2.2 Preparation and Administration

6.2.2.1 Intramuscular Administration

The volumes for IM administration are provided by participant weight range and indication in [Table 8](#). AZD8895 and AZD1061 (comprising AZD7442), must both be administered separately to the participant in sequential order, with no participant receiving doses of AZD8895 without also receiving the matching dose of AZD1061.

Accurately withdraw the required volume for each of the injections. Use a single disposable polycarbonate or polypropylene syringe for each of the injections.

Administer the injections of AZD7442 (comprised of AZD8895 and AZD1061) using a needle of appropriate gauge and length for each of the injections, according to standard procedures for IM injections for patients in each weight bracket. AZD8895 should be administered first in the anterolateral thigh followed by administration of AZD1061 in the alternate anterolateral thigh.

Table 8 Volume of AZD7442 for IM Administration by Participant Weight Range and Indication

Participant weight range (kg)	Dose	Injection volume (mL) of AZD8895 100 mg/mL	Injection volume (mL) of AZD1061 100 mg/mL	Total injection volume (mL) of AZD7442 100 mg/mL (AZD8895 + AZD1061)
Prophylaxis of COVID-19 (Cohort 1)/Treatment of mild to moderate COVID-19 (Cohort 2)				
≥ 1.5 to < 5 kg	60 mg (30 mg AZD8895 and 30 mg AZD1061)	0.3	0.3	0.6
≥ 5 to < 15 kg	150 mg (75 mg AZD8895 and 75 mg AZD1061)	0.75	0.75	1.5
≥ 15 to < 40 kg	Participants in this weight range will be administered AZD7442 via IV infusion			
≥ 40 kg	600 mg (300 mg AZD8895 and 300 mg AZD1061)	3	3	6

AZD8895 must be administered first followed by AZD1061.

COVID-19, coronavirus disease 2019; IM, intramuscular; IV, intravenous.

6.2.2.2 Intravenous Administration

AZD7442 is dosed by co-administration of AZD8895 and AZD1061 in a single IV infusion.

The dose volume to be administered to each participant depends on the weight of the participant, the indication (ie, prophylaxis, inpatient, or outpatient treatment), and the concentration of the prepared dilution as indicated in [Table 9](#) and [Table 10](#). The dose of AZD7442 (AZD8895 and AZD1061) should be administered as an admixture of AZD7442 (AZD8895 and AZD1061) and diluent. The diluent is to be selected per the standard of care of the participant and may consist of 0.9% sodium chloride for injection or 5% dextrose for injection.

Dose Preparation

AZD7442 (AZD8895 and AZD1061) for administration should be prepared by combining the required volume of AZD7442 (AZD8895 and AZD1061) with an appropriate volume of diluent to give a final AZD7442 admixture with a concentration ranging from 10 mg/mL to 50 mg/mL. Refer to [Table 10](#) for recommended volumes for AZD7442 (AZD8895 and AZD1061) and diluent in order to achieve the required concentrations. The AZD7442 admixture should be prepared by following the procedure below:

- Withdraw the AZD7442 (AZD8895 and AZD1061) dose volume into a suitable size syringe. Prepare a separate syringe containing required amount of diluent.
- Transfer the AZD7442 (AZD8895 and AZD1061) solution into the diluent syringe; once capped (or secured with an attached needle), mix the solution using gentle inversion. Do not shake.

Table 9 Preparation of AZD7442 Admixture for IV Administration

Concentration of AZD7442 Admixture (mg/mL)	Number of AZD8895 (100 mg/mL) vials required	Number AZD1061 (100 mg/mL) vials required	AZD8895 Volume for Dilution (mL)	AZD1061 Volume for Dilution (mL)	Diluent volume for dilution (mL)	Total volume post-dilution (mL) ^a
10	1	1	1.5	1.5	27	30
20	1	1	1.5	1.5	12	15
50	1	1	1.5	1.5	3	6
50	2	2	3.0	3.0	6	12

^a The volume of the prepared diluted AZD7442 admixture will exceed the volume that will be required for dose administration

IV, intravenous.

Dose Administration

Following dilution, the required volume of the AZD7442 admixture for the intended dose will be drawn into an appropriately sized syringe or IV bag and administered intravenously. Refer to [Table 10](#) for the volume of admixture to be administered.

The dose volumes, infusion rates, and infusion times for each weight range were determined by considering the maintenance fluid rate and maintenance volume requirements. It is not recommended to deviate from these values unless the participant has a particular medical requirement that deems it necessary to adjust.

- AZD7442 (AZD8895 and AZD1061) infusion is to be administered through an IV administration set with a 0.2 or 0.22 µm low protein binding filter; acceptable configurations include an IV set containing an in-line filter or the attachment of a separate filter to the distal end of the IV tubing.
- AZD7442 (AZD8895 and AZD1061) infusion can be administered through the same IV line as other medications when local practices for flushing the line with each administration are followed.
- Administration set volume should not exceed 2 mL in order to minimize the flush volume.

- The IV line and catheter will be flushed according to local practices to ensure the full dose is administered. It is recommended to flush at the same rate as the drug infusion rate (listed in [Table 10](#)).
- **Important:** The timing of the PK sample must be well coordinated such that the PK sample is immediately obtained after the full dose is delivered. Sampling should occur immediately after the IV line and catheter are flushed.

The approximate infusion time and target rates are listed in [Table 10](#); however, if there are interruptions, the total allowed time must not exceed 4 hours with the infusion syringe maintained at room temperature, otherwise a new dose must be prepared from new vials.

Table 10 Doses and AZD7442 Admixture Concentration Selection per Cohort and Participant Weight Range for IV Administration

Participant weight range (kg)	Dose of AZD7442 (mg)	Concentration of AZD7442 Admixture (mg/mL) ^a	Volume of AZD7442 Admixture for administration (mL)	Infusion rate (mL/minute; mL/hour)	Approximate infusion time (minutes) ^b
Prophylaxis (Cohort 1)/Treatment – Outpatient (Cohort 2)					
≥ 1.5 to < 5 kg	50	20	2.50	0.1 mL/min; 6.0 mL/hour	25
≥ 5 to < 15 kg	110	50	2.20	0.3 mL/min; 18 mL/hour	7
≥ 15 to < 40 kg	300	50	6.00	0.8 mL/min; 48 mL/hour	8
≥ 40 kg	440	50	8.80	1.0 mL/min; 60 mL/hour	9
Treatment – Inpatient (Cohort 3)					
≥ 1.5 to < 5 kg	60	20	3.00	0.1 mL/min; 6 mL/hour	30
≥ 5 to < 15 kg	150	50	3.00	0.3 mL/min; 18 mL/hour	10
≥ 15 to < 40 kg	400	50	8.00	0.8 mL/min; 48 mL/hour	10
≥ 40 kg	600	50	12.00	1.0 mL/min; 60 mL/hour	12

^a Refer to [Table 9](#) for instructions on preparation of the AZD7442 admixture.

^b Infusion time does not account for flush time

AZD7442 is to be administered as a single IV infusion (AZD8895 and AZD1061 co-administered).

IV, intravenous; min, minute.

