6.4 Study Intervention Compliance

When the individual dose for a participant is prepared from a bulk supply, the preparation of the dose will be confirmed by a second member of the study site staff.

Dosing will take place under the guidance of study personnel, and may occur at study sites, mobile units, or other health care facilities. The date, and time if applicable, of dose administered will be recorded in the source documents and recorded in the eCRF. The dose of study intervention and study participant identification will be confirmed at the time of dosing by a member of the study site staff other than the person administering the study intervention. If a problem occurs during dosing, such as needle break, no re-dosing is permitted.

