7 DISCONTINUATION OF STUDY INTERVENTION AND PARTICIPANT DISCONTINUATION/WITHDRAWAL

7.1 Discontinuation of Study Intervention

Participants will receive a single IM dose of AZD7442 (administered as a single IM injection containing AZD8895 followed by a single IM injection containing AZD1061) or a single IV

dose of AZD7442 (administered by co-infusion of AZD8895 and AZD1061 in the same bag).

It may be necessary for a participant to temporarily interrupt their injection/infusion of IMP. If the injection of IMP is not resumed (ie, it is discontinued), the participant should remain in the study to be evaluated.

Note that discontinuation of IMP is NOT the same thing as withdrawal from the study.

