8.4 Overdose

For this study, any dose of AZD7442 greater than a planned weight-based dose presented in [Table 6](#) will be considered an overdose.

AstraZeneca does not recommend a specific treatment for an overdose. Symptoms of overdose should be treated as per clinical judgment.

- An overdose with associated AEs is recorded as the AE diagnosis/symptoms on the relevant AE modules in the eCRF and on the Overdose eCRF module.
- An overdose without associated symptoms is only reported on the Overdose eCRF module.

If an overdose on an AstraZeneca study intervention occurs during the study, the Investigator or other site personnel inform appropriate AstraZeneca representatives immediately, but **no later than 24 hours** of when he or she becomes aware of it.

The designated AstraZeneca representative works with the Investigator to ensure that all relevant information is provided to the AstraZeneca Patient Safety data entry site **within one or 5 calendar days** for overdoses associated with an SAE (see [Section 8.3.9](#)) and **within 30 days** for all other overdoses.

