#### **4.1.3 Protocol Deviations**

##### **4.1.3.1 Definitions and Derivations**

Important deviations from the protocol (IPDs) may lead to the exclusion of participants or data from the PKS or SES. Deviations will be assessed and classified during the study and finalized before database lock. IPDs include those deviations from the protocol that are likely to have an impact on the perceived safety of study treatments or outcome assessment.

IPDs will include the following at a minimum:

- Violation of key inclusion and/or exclusion criteria.
- Administration of prohibited concomitant medications that are expected to influence the outcome of this study.
- Deviations from planned dose or administration procedure of the IMP.
- Relevant time window deviations expected to influence key safety and/or PK assessments.

All important protocol deviations will be listed. A qualitative summary table will be provided.

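### Protocol 6.2.2.2 and 6.4 point in opposite directions for an infusion interrupted part-way and held beyond 4 hours, and nothing says how the amount already infused counts

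*Protocol*

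**What the plan says.** **Protocol 6.2.2.2 (Intravenous Administration):** if the infusion is interrupted, the total time is capped at 4 hours "with the infusion syringe maintained at room temperature, otherwise a new dose must be prepared from new vials". The sentence does not mention drug already infused.

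**Protocol 6.4 (Study Intervention Compliance):** "If a problem occurs during dosing, such as needle break, no re-dosing is permitted". A needle break is the only example of a problem.

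**Protocol 8.4 (Overdose):** an overdose is "any dose of AZD7442 greater than a planned weight-based dose" in Table 6.

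Other sections touch on the situation:
- **6.2.1** sets a hold time of 4 hours at room temperature or 24 hours refrigerated, but for a different interval: "Total time from needle puncture of the vial to the start of administration must not exceed" these limits.
- **7.1** foresees the event: "It may be necessary for a participant to temporarily interrupt their injection/infusion of IMP". It adds that a participant whose dosing is not resumed stays in the study.
- **7.4.1** provides full follow-up after a partial dose.
- **Appendix F, Table 19** has sites hold administration for mild and some moderate reactions and lets the investigator resume.
- **SAP 4.1.3.1** counts "Deviations from planned dose or administration procedure of the IMP" among the important deviations, which may lead to exclusion from the PK or neutralizing-antibody analysis set.
- **SAP 4.2.8.1** lists planned dose, administered dose and medication errors during administration, and names interruptions as an example of such errors.

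**The concern.** For a part-delivered infusion past the 4-hour limit, one section calls for a new dose to be made up and another bars giving more after a dosing problem. Two sites could read the same pages and give two children in the same weight band different totals.

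The first stake is participant safety, because the amount received depends on which section the site follows. The second is classification: the same event could be a partial dose, a completed dose or an overdose. The third is the PK analysis. SAP Table 3 computes IV clearance as dose over AUC and Vss as MRT times clearance, without saying whether planned or administered dose is meant. The full analysis set has only 46 participants (SAP Section 2), so one misclassified child can affect a small weight-by-route cell.

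**Working it through.** **1. Reproduce Table 10.** Volume = dose / admixture concentration; time = volume / rate.

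| Cohort, band | Calculation | Minutes | Table 10 |
|---|---|---|---|
| 1/2, 1.5 to <5 kg | 50/20 = 2.5 mL; 2.5/0.1 | 25 | 25 |
| 1/2, 5 to <15 kg | 110/50 = 2.2 mL; 2.2/0.3 | 7.33 | 7 |
| 1/2, 15 to <40 kg | 300/50 = 6 mL; 6/0.8 | 7.5 | 8 |
| 1/2, ≥40 kg | 440/50 = 8.8 mL; 8.8/1.0 | 8.8 | 9 |
| 3, 1.5 to <5 kg | 60/20 = 3 mL; 3/0.1 | 30 | 30 |
| 3, 5 to <15 kg | 150/50 = 3 mL; 3/0.3 | 10 | 10 |
| 3, 15 to <40 kg | 400/50 = 8 mL; 8/0.8 | 10 | 10 |
| 3, ≥40 kg | 600/50 = 12 mL; 12/1.0 | 12 | 12 |

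All volumes match exactly, and all times match after rounding.

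**2. How long an interruption breaches the limit.** If the clock starts with the infusion, finishing within 240 minutes becomes impossible once the interruption exceeds 240 minus the infusion time. That is 240 − 30 = 210 minutes for the longest infusion and 240 − 7.33 = 232.7 minutes for the shortest, or about 3.5 to 3.9 hours. If the clock starts at vial puncture, a shorter interruption suffices. Section 6.2.2.2 does not say when it starts.

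**3. What the child could receive.** Let D be the planned dose and f the fraction infused before the interruption (0 < f < 1). The documents give no value for f, so it is shown as a range.
- Nothing more given: f × D
- Remainder only: f × D + (1 − f) × D = D
- Whole new dose: f × D + D = (1 + f) × D

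| D (mg) | f | Nothing more | Remainder only | Whole new dose |
|---|---|---|---|---|
| 50 | 0.1 | 5 | 50 | 55 |
| 50 | 0.5 | 25 | 50 | 75 |
| 50 | 0.9 | 45 | 50 | 95 |
| 440 | 0.1 | 44 | 440 | 484 |
| 440 | 0.5 | 220 | 440 | 660 |
| 440 | 0.9 | 396 | 440 | 836 |

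The third total always exceeds D and approaches 2D without reaching it.

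**4. Does another section settle it?** Section 6.2.1 stops at the start of administration, when nothing has been given. Sections 7.1 and 7.4.1 accept interruption and partial dosing but do not mention a newly prepared dose. Table 19 speaks of resuming the current administration, not of replacing an expired syringe. Table 10 gives only whole-dose volumes. Section 8.4 classifies an excess but does not say what to give. None of them answers the question.

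**5. Effect on clearance.** Assume linear PK, so that AUC is proportional to the delivered dose k × D. If the planned dose D were entered, calculated CL would be D / (k × D / CL) = CL / k. For k = 0.5 that is 2 × CL; for k = 1.5 it is 0.67 × CL. Vss scales in the same way if MRT is unchanged. Entering the administered dose removes the error.

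**The case against.** The strongest reply is that the two sections deal with different things. Section 6.2.2.2 reads as a product hold-time rule: Section 6.2.1 attaches the same instruction to make up a new dose to its own storage limits, with the same 4-hour room-temperature figure. Section 6.4 illustrates a problem by a needle break, which is an injection failure, while interruption has its own text in 7.1. On that view there is no conflict.

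This is a possible reading, but the documents do not state it. Section 6.2.2.2 carries the hold-time instruction into a period when drug may already have been given. SAP 4.2.8.1 treats an interruption as a kind of medication error during administration, so placing it within the scope of 6.4 is not far-fetched.

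A reader might also infer that 6.2.2.2, followed literally, orders an overdose, or that children would receive almost twice the planned dose. The documents do not support that. The section says a new dose is *prepared*; it does not say the whole of it is infused on top of what was given. It separates preparation from administration, and Table 9 notes that the prepared volume exceeds what is administered. Section 6.1.1 specifies a single dose, and 8.4 marks anything above plan as an overdose. Nearly doubling would also need almost the whole dose delivered first: for 440 mg at f = 0.9, only 0.1 × 8.8 = 0.88 minutes of infusion remain.

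Two further points stand. SAP 4.2.8.1 already lists the administered dose, so the data requirement is largely met. SAP Section 2 says enrolment was discontinued and Cohort 3 is empty, which limits the practical effect of new dosing wording in this trial.

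**Conclusion.** The conflict is real, for a narrow case: an IV infusion interrupted after partial delivery and held beyond 4 hours at room temperature. The text leaves open totals of f × D, D and (1 + f) × D, and no section chooses among them. The last is left open by silence rather than instructed, and twice the planned dose is a limit that is never reached.

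The event should be rare given infusions of about 7 to 30 minutes. The documents give no frequency, so none is claimed. The conclusion assumes that an interrupted infusion can count as a problem during dosing under 6.4; the wording permits this and SAP 4.2.8.1 makes it plausible. Two dosing instructions that point in opposite directions bear on safety and should be reconciled even for a rare event. The unspecified dose in SAP Table 3 is a minor matter.

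**What to change.** Reconcile Protocol 6.2.1, 6.2.2.2, 6.4, 7.1, 7.4.1 and 8.4 into one consistent statement for an infusion interrupted beyond the allowed time. It should say which instruction governs, when the 4-hour clock starts, and how the amount already infused counts toward the Table 6 dose. Which rule is right is a clinical decision for the sponsor and is not proposed here.

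As a minor clarification, state in SAP Table 3 that CL and Vss use the administered dose already listed under SAP 4.2.8.1. With enrolment closed, the useful step for the existing data is to check that exposure listing for interrupted or part-delivered infusions before the PK parameters are derived.

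The cost is protocol wording and one SAP clause, with no new procedure or data collection.
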